For subjects with MCL, DLBCL, FL, CLL (except for the CLL dose ranging cohort), a Bayesian, continuous data review, which will be conducted independently, will be used to update the estimates of progression-free survival (PFS) rates at 16 weeks (CLL after BCR targeted therapy, MCL and DLBCL) or 24 weeks (CLL and FL), assessing the efficacy once each subject's primary endpoint becomes available for a cohort. Because it consists of 3 different histologies, accrual to the 'non-FL iNHL' cohort will continue to a maximum of 45 subjects without interim review. The continuous data review for MCL, DLBCL, FL and CLL cohorts (except for the CLL dose ranging cohort) will be conducted independently. Futility assessment will begin when the first eligible 10 subjects' primary endpoints become available.

Given the initial activity seen in the CLL cohort, which was treated with the original formulation, and improved PK of the new formulation, exploration of lower doses will be pursued in the 3 CLL cohorts {[Sharman 2015](#)}. Subjects who are treated at lower doses of GS-9973

SDD may have their dose escalated up to 400 mg (200 mg x 2) BID, if after 8 weeks there is less stable disease or at the time of disease progression, if the investigator feels it is in the subject's best interest.

Up to 40 subjects will be studied in each cohort of MCL, DLBCL, FL and CLL, up to 45 subjects will be enrolled in the non-FL iNHL cohort; up to 60 subjects will be enrolled in each cohort of CLL dose ranging, CLL prior BTK inhibitor exposure and CLL prior PI3K inhibitor exposure).

In the BCR targeted therapies cohorts, subjects who have progressed will be enrolled to either simple progression (Non-Richter's) or transformation (Richter's) to Richter's or Richter's-like disease. A biopsy is not required but encouraged if there is a clinical concern of possible transformation. In each BCR targeted therapies sub-cohort a) progression (Non- Richter's) or b) transformation (Richter's), a separate futility assessment will occur after the first 10 subjects are accrued in each sub-cohort. Thereafter, continuous data review may be conducted when a new primary endpoint becomes available.

- If the futility criterion is not met, subsequent subjects will be enrolled until a total number of 20 (Richter's) or 40 (Non-Richter's) subjects per cohort. The CLL subjects who were previously treated with BCR inhibitors will be recruited for a cohort dosed at 400 mg twice daily (BID) of GS-9973 SDD.

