5.3.6. Management of Dose Limiting Toxicities

Adverse events and laboratory abnormalities will be graded using the CTCAE, Version 4.03. Dose modification of GS-9973/GS-9973 SDD should be performed for the following dose limiting AEs:

- Grade 4 hematological toxicities persisting for ≥ 14 days
- Grade ≥ 3 toxicities of other types

Of note, the occurrence of asymptomatic lymphocytosis will not be considered a toxicity requiring dose modification. Dose reduction will not be required for untreated vomiting, diarrhea, or constipation; interruption of dosing until these symptoms are adequately treated is permitted.

Table 5-2. GS-9973 MM Dose Levels

Dose Level	GS-9973 MM Dose (mg BID fasting)
0	800
-1	600
-2	400
-3	200

Table 5-3. GS-9973 SDD Dose Levels

Dose Level	GS-9973 SDD Dose (mg BID fasting)
CLL Prior BTK inhibitor Exposure, CLL Prior PI3K inhibitor Exposure or CLL Dose Ranging randomized to 400mg BID or Dose level 0	400
CLL Dose Ranging randomized to 200mg BID or Dose level -1	200
CLL Dose Ranging randomized to 100mg BID or Dose level -2	100

If a subject experiences an AE or laboratory abnormality that is suspected to be related to GS-9973/GS-9973 SDD, and requires a dose reduction, GS-9973/GS-9973 SDD administration should be interrupted, as necessary, until the AE or laboratory abnormality resolves or stabilizes to an acceptable degree (generally to Grade 1 or the pretreatment severity grade, whichever is higher). More frequent monitoring (eg, once per week) may be warranted until adverse events or laboratory abnormalities are clearly improving. When treatment is reinstated, the dose of GS-9973/GS-9973 SDD should be reduced by 1 dose level (see [Table 5-2](#) and [Table 5-3](#)).

Successive adjustments to progressively lower dose levels can be made. If the subject cannot tolerate GS-9973/GS-9973 SDD at the lowest dose level then the subject should discontinue GS-9973/GS-9973 SDD therapy.

After a dose is reduced, the dose need not be re-escalated, even if there is minimal or no toxicity with the reduced dose. However, if the subject tolerates a reduced dose of GS-9973/GS-9973 SDD for ≥ 4 weeks then the GS-9973/GS-9973 SDD dose may be increased to the next higher dose level, at the discretion of the investigator. Such re-escalation should strongly be considered if further evaluation reveals that the AE that led to the dose reduction was not GS-9973/GS-9973

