SDD-related. Successive adjustments to progressively higher dose levels can be made at 4-week intervals up to the highest dose level. Dose escalations above the highest dose level are not allowed. Any study drug dose re-escalation must be discussed between the investigator and the Gilead Sciences Medical Monitor or designee prior to implementation.

Whenever the study drug dose is de-escalated or re-escalated, the appropriate clinic staff should dispense the study drug for the new dose level and instruct the subject/caregiver about the change in dose level.

Note: Dose modifications and clinical management for subjects who enter the study with pre-existing Grade 3 or 4 abnormalities due to their underlying malignancy will be discussed with the study Medical Monitor or designee prior to the initiation of treatment.

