6.6. At Disease Progression

All subjects will be followed until initiation of next treatment. If the subject was not receiving study drug at the time tumor progression was documented, or was at a dose level below the maximum and could potentially tolerate a higher dose, after discussion with the Gilead Sciences Medical Monitor, the subject may continue on study and study drug may be re-started or escalated using the algorithm defined in Section [5.3.5](#) if the investigator feels it is in the subject's best interests to do so.

If the investigator feels the subject is having progressive disease, tumor imaging as described in Section 6.12 should be carried out unless the most recent imaging had documented progressive disease. The images and any other material needed to document progression are to be transferred to the IRC as soon as possible. While waiting for confirmation of progressive disease from the IRC, the subject should continue to receive study drug unless his/her medical condition warrants immediate treatment with different therapy. When progression is confirmed, the following procedures should be carried out while the subject is still receiving study drug.

- Complete physical examination including weight
- Vital signs including blood pressure, respiratory rate, pulse, oxygen saturation by pulse oximetry, temperature
- Karnofsky performance status (see Section 6.9.3)
- Concomitant Medication Review
- Obtain blood samples for:
 - Chemistry (see Section 6.9.8)
 - Hematology (see Section 6.9.8)
 - Coagulation (see Section 6.9.8)
 - GS-9973/GS-9973 SDD plasma concentration (excluding subjects off study drug at time of progression)

For subjects with SLL, CLL or MCL

- CTC Molecular characterization (see Section 6.14)
- Cytokines and chemokines (see Section 6.13.1)
- CTC RNA pre-dose (see Section 6.13.2)

CCI

- Record the approximate number of hours between the last 2 doses of study drug and the time the blood samples for plasma concentration were obtained (excluding subjects off study drug at time of progression)
- Urine pregnancy test (females of childbearing potential)

- For CLL subjects a bone marrow biopsy/aspirate will be collected to confirm a PD. If the nature of PD does not require bone marrow confirmations, it is not necessary to obtain a bone marrow biopsy/aspirate (See Section [6.20](#)).
- Collect used/unused study drug and assess study drug compliance by pill counts (excluding subjects off study drug at time of progression)

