8.4.2. Calculation of Tumor Control Variables

Tumor control assessments will be based on standardized response and progression criteria for NHL {Cheson 2007} and CLL {Hallek 2008}, as specifically modified for this study considering the pharmacology of GS-9973 {Cheson 2012}. The individual and composite endpoints of response and progression (considering changes in lymph node area, liver and spleen size, bone marrow, platelet counts, hemoglobin, neutrophil counts, and peripheral blood lymphocyte counts) will be determined. Tumor control will be documented at each assessment by response category (eg, CR, PR, SD, definitive PD) as defined for each response parameter, SPD value, percentage change in SPD values from baseline or nadir, date that response is first documented, date that response is confirmed, and date of disease progression.

Changes in tumor status as provided by the investigator and changes in tumor status as adjudicated by the IRC (see Section 9.4) will be described and compared. The findings of the IRC will be considered primary for analyses of all tumor control endpoints.

For time-to-event endpoints of PFS and DOR, the following censoring conventions will be applied:

- Data from surviving, non-progressing subjects will be censored at the earliest of the time of initiation of antitumor treatment other than the study treatment or the last time that lack of definitive progression was objectively documented.
- Data from subjects who have disease progression or die after ≥ 2 consecutive missing tumor assessments will be censored at the last time prior to the missing assessments that lack of definitive disease progression is objectively documented.

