## **6. EFFICACY ANALYSES**

### **6.1. Primary Efficacy Endpoint**

#### **6.1.1. Definition of the Primary Efficacy Endpoint**

The primary efficacy endpoint of this study is PFS rate at 16 weeks (CLL after BCR targeted therapy, MCL, and DLBCL) or 24 weeks (CLL and iNHL). PFS is defined as the interval from the first dose of ENTO to the earlier of the first documentation of definitive disease progression or death from any cause.

The determination of NHL response and progression (defined in the Protocol Section 6.20) is based on standardized criteria {Cheson 2007, Rourke 2010} as specifically modified for this study to reflect the biology of the diseases under study and the pharmacology of ENTO and the methods to be used in evaluation. The determination of CLL response and progression (defined in the Protocol Section 6.21) is based on standardized IWCLL criteria {Hallek 2008} as specifically modified for this study considering the pharmacology of ENTO and the methods to be used in evaluation.

In accordance with the Gilead Protocol 339-0102 Imaging Charter, if there is uncertainty regarding whether there is true progression, the subject may continue study treatment and remain under close observation (eg, evaluated at 4-week intervals). If subsequent evaluations suggest that the subject is experiencing progression, then the date of progression should be the time point at which progression was first identified. A single PD determination followed by a determination that indicated either no change or improvement in disease prior to the single PD observation will not be considered as PD.

Subjects without progression or death will be censored at the last adequate post-baseline tumor assessment time. If subjects receive other anti-cancer therapy or have  $\geq 2$  consecutive missing post-baseline tumor assessments immediately before documented progression or death, they will be censored at the last adequate post-baseline tumor assessment time before starting anti-cancer therapy or before  $\geq 2$  consecutive missing tumor assessments whichever is earlier. If subjects don't have adequate baseline tumor assessment or adequate post-baseline tumor assessment, they will be censored on the date of Study Day 1 unless subjects die before or on the 2nd scheduled post-baseline tumor assessment without receiving other anti-cancer therapy. Please see [Appendix 2](#) for details on PFS event and censoring time derivation.

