## **6.2. Secondary Efficacy Endpoint**

### **6.2.1. Definition of Secondary Efficacy Endpoints**

Same as the primary efficacy endpoint analysis, the response assessments by IRC will be used for the secondary efficacy endpoints' analyses based on the FAS. The response assessments after other anti-cancer therapy (if they are available) won't be included for secondary efficacy endpoints analyses.

- Objective response rate (ORR).

Best overall response (BOR) of complete response (CR), partial response (PR), stable disease (SD), progressive disease (PD), not evaluable (NE), no disease (ND), and not applicable (NA) is allowed. For subjects with LPL/WM, a very good partial response (VGPR) or minor response (MR) is also allowed. Again, a single PD determination followed by a determination that indicated either no change or improvement in disease prior to the single PD observation will not be considered as PD.

ORR is defined as the proportion of subjects with BOR during ENTO therapy of CR or PR (or VGPR or MR for subjects with LPL/WM). Subjects who do not have sufficient baseline tumor assessment, whose on-study tumor status information is not adequate for response status assessment or who received new anti-cancer therapy prior to achieving CR or PR (or VGPR or MR for subjects with LPL/WM), will be considered as non-responders.

- Duration of response (DOR).

DOR is defined as the interval from the first time when the objective response (CR or PR [or VGPR or MR for subjects with LPL/WM]) is achieved to the earlier of the first documentation of definitive disease progression or death from any cause.

- Time to response (TTR).

TTR is defined as the interval from the first dose of ENTO to the first time when the response (CR or PR [or VGPR or MR for subjects with LPL/WM]) is achieved.

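### In the randomised CLL dose-ranging cohort, the SAP's single-PD rule does not require the overturning scan to precede a dose increase, so a PD on 100 or 200 mg could be removed by a scan on a higher dose

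*SAP*

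**What the plan says.** **The rule.** SAP 6.1.1 describes the NHL and CLL criteria together, then gives a paragraph on doubtful progression that cites the Imaging Charter. It ends: "A single PD determination followed by a determination that indicated either no change or improvement in disease prior to the single PD observation will not" count as PD. SAP 6.2.1 says again, for best overall response, that "a single PD determination followed by a determination that indicated either no change or improvement in disease prior to the single PD observation" does not count. Neither section limits the rule by disease, by cohort or by the dose at the later scan.

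**Its source.** In the protocol, the cancelling sentence appears only in the NHL criteria (6.20.7.7). The CLL criteria (note to 6.21.5.4) date persistent definitive progression to its first objective documentation and refer uncertain cases to the IRC. They contain no cancelling sentence.

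**Dose increases.** The protocol synopsis (Study Design) lets subjects on lower SDD doses go up to 400 mg BID "if after 8 weeks there is less stable disease or at the time of disease progression", if the investigator thinks it in the subject's interest. Protocol 6.6 lets a subject who "was at a dose level below the maximum and could potentially tolerate a higher dose" remain on study and be escalated at documented progression, after discussion with the medical monitor. It adds: "While waiting for confirmation of progressive disease from the IRC, the subject should continue to receive study drug", unless the subject's condition calls for other therapy at once. Protocol 5.3.6 states "Dose escalations above the highest dose level are not allowed". It also says that after at least 4 weeks on a tolerated reduced dose, the "dose may be increased to the next higher dose level, at the discretion of the investigator".

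**Censoring and attribution.** Protocol 8.4.2 censors at "initiation of antitumor treatment other than the study treatment". SAP Appendix 2 and Table 13-1 refer to new anti-cancer therapy. SAP 3.1.2 groups the full analysis set by planned treatment, and SAP 6.1.2 estimates PFS in this cohort by dose level.

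**The concern.** In a dose-ranging comparison, progression on the assigned dose is the failure to be counted. Here that failure can itself lead to a higher dose of the same drug. If disease then shrinks back on the higher dose, the single-PD rule as written lets that scan erase the earlier failure, and the success is credited to the lower dose.

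This is the study's only randomised allocation to dose, and the by-dose Week 24 PFS rate is its primary result. The error would mainly raise the 100 and 200 mg estimates and so narrow the apparent difference from 400 mg. Best response is affected in the same way. Protocol 6.21.5 takes the best response up to progression, so a cancelled PD leaves the window open and a response reached on the higher dose can enter the lower-dose ORR.

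No planned summary would show this. SAP 4.2.1 counts dose modifications without separating increases, and SAP 6.3 drops the sensitivity analyses. A case could be traced only by hand, by setting the dosing listings (SAP 4.2.2) against the response listings (SAP 6.2.2.1).

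**Working it through.** **1. Is the path open on the text?**
- *Timing.* Protocol 6.5 schedules scans at Weeks 8, 16 and 24. A PD at Week 8 leaves two scheduled scans up to and including Week 24; a PD at Week 16 leaves one.
- *Increase.* Permitted at progression (synopsis; Protocol 6.6). It is also permitted after 8 weeks on the investigator's assessment, and there the synopsis does not require an IRC-confirmed PD.
- *Censoring.* A higher dose of entospletinib is neither treatment other than study treatment nor new anti-cancer therapy, so follow-up continues.
- *Cancellation.* A later scan showing disease no worse than before the PD meets the SAP sentence, whatever the dose at that scan.
- *Attribution.* The subject is still counted in the planned 100 or 200 mg arm.

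No step is blocked. Table 13-1 does not settle the matter: it dates the event at the first documented progression and says nothing about a PD later reversed. A programmer working from Table 13-1 and one working from SAP 6.1.1 could derive different PFS times for the same subject.

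**2. Arm size.** Protocol 8.7 gives 60 subjects, 20 per dose: 3 × 20 = 60, which agrees.

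**3. Effect of one case.** Suppose the subject then stays progression-free and uncensored through Week 24. The Kaplan-Meier rate is a simple proportion, and one case adds 1/20 = 5 points; k cases add 5k points. The documents give no means of deriving k.

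**4. Example with the SAP's log-log interval** (the starting rate of 14/20 is assumed). For d events in n = 20 without censoring, S = 1 − d/n, the Greenwood variance of log S is d/[n(n − d)], and the standard error on the log-log scale is √{d/[n(n − d)]}/|log S|.
- d = 6: S = 0.70; √(6/280) = 0.146; 0.146/0.357 = 0.410; 95% CI 45.1% to 85.3%.
- d = 5: S = 0.75; √(5/300) = 0.129; 0.129/0.288 = 0.449; 95% CI 50.0% to 88.7%.

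The intervals are 40.2 and 38.7 points wide.

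**5. Scale against a difference between two arms of 20.** SE = √[2p(1 − p)/20], with the same true rate p assumed in both arms.

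| p (assumed) | SE (points) | 5 points / SE |
|---|---|---|
| 0.5 | 15.8 | 0.32 |
| 0.6 | 15.5 | 0.32 |
| 0.7 | 14.5 | 0.35 |
| 0.8 | 12.6 | 0.40 |

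**The case against.** The strongest reply is that the two situations hardly meet. The SAP paragraph opens with uncertain progression, whereas Protocol 6.6 allows escalation once progression is documented. The instruction to stay on drug while the IRC decides concerns continuing the drug, not increasing it. PFS rests on IRC reads, so an investigator's decision to escalate does not by itself create a PD that could be cancelled. The overturning scan must show disease no worse than before the PD, which for a 50% increase from nadir or a new node means near-complete reversal. The Imaging Charter may also restrict which scans can overturn a PD. Finally, the study is exploratory, no formal dose comparison is planned, and the report will be synoptic.

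Most of this stands as a limit on how often the problem can arise. It does not close the path. The cancelling sentence itself carries no condition of uncertainty or of unchanged dose, and any restriction in a charter outside these documents should also appear in the SAP.

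Three stronger readings are tempting, and the documents do not support them.
- *That escalation after progression routinely wipes out low-dose failures.* Nothing in the documents gives a frequency, and the conditions above suggest that it is uncommon.
- *That the bias runs strictly one way.* A 400 mg subject whose dose was reduced can be raised again, so that arm is not wholly exempt.
- *That the SAP flatly contradicts the protocol for CLL.* By dating only persistent progression, the protocol's CLL note leaves room for a PD that does not persist. What is missing is a stated rule for cancelling one, and SAP 6.3 does not record that the SAP supplies it.

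A further objection is that a subject escalated without any IRC PD also brings higher-dose follow-up into the lower-dose arm. That is true, but it follows from analysing by planned treatment and is a separate matter.

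**Conclusion.** The gap is real and of minor to moderate importance. Followed as written, the SAP can turn a failure on 100 or 200 mg into a success because of a scan taken on a higher dose, both in the Week 24 PFS rate and in best response. Each case is worth 5 points in an arm of 20, or 0.32 to 0.40 of the standard error of a two-arm difference for assumed true rates of 50% to 80%. That is modest beside the width of the intervals. The 5 points assume that the subject is uncensored and stays progression-free to Week 24, and the total effect depends on a case count that cannot be derived. No figure stated in the plan is wrong. A reader might infer that the by-dose results would be unreliable as a whole; the documents do not support that. The case for acting is that the direction mainly favours the lower doses, the planned tables would not reveal it, and the remedy is cheap.

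**What to change.** In SAP 6.1.1, 6.2.1 and Appendix 2, with a matching row in Table 13-1, state that in the dose-ranging cohort, in all three arms alike, an IRC PD may be cancelled only by an assessment made before any dose increase that follows that PD. Otherwise the PD stands on its own date and closes the best-response window. Do not extend this to a restart at the same dose after an interruption: the note to Protocol 6.21.5.4 says that worsening during a temporary interruption does not necessarily mean resistance.

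Say explicitly whether the single-PD rule applies to CLL, reconcile it with Protocol 6.21.5.4 and with the Imaging Charter, and record the change in SAP 6.3.

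Report per arm the number of PDs followed by a dose increase and the number of those that the rule as now written would have cancelled. Show the by-dose Week 24 rate under that rule as one supporting figure, named in SAP 6.3 as an exception because that section now rules out sensitivity analyses.

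The cost is a few sentences, one table row, one flag built from dosing data already collected, and one extra rate per arm. The downside is that an occasional false PD followed by escalation is kept as an event, mainly in the lower-dose arms, at 5 points each. The supporting figure shows how much this matters. No change to the escalation rules is proposed. The protocol should, however, reconcile its own cross-reference: 6.6 points to 5.3.5 for the escalation algorithm, but 5.3.5 covers the change of formulation.
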